Title page

Process-based Therapy vs. routine-CBT for difficult-to-treat mood and anxiety disorders:
Study protocol for a randomized controlled trial

Names protocol contributors

[name] [contact], [name] [contact], [name] [contact], [name] [contact], [name] [contact], [name] [contact], [name] [[contact]](mailto:[contact]), [name] [contact] & [name] [contact]

All authors at: Institute for Psychology - Department of Clinical Psychology and Psychotherapy, Goethe University Frankfurt, [name], Germany; except: [name], Department of Clinical Psychology and Psychotherapy, Philipps University Marburg, [name], Germany

Paper submitted to: Trials

Abstract

Background:

Process-based Therapy (PBT) is a new framework to intervention planning, based on the use of ecological momentary assessment (EMA) data and dynamic and idiographic network analyses. Support for its applicability has been reported from a single-case studies. Here, we examine the feasibility and effectiveness in a larger clinical sample. We have translated a Training Manual of PBT and modified for delivery of CBT in Mental Health Service. The aim of this study is to test the relative efficacy of PBT compared to traditional CBT delivered in routine practice (r-CBT) for difficult-to-treat mood and anxiety disorders.

Methods:

The study is a randomized controlled trial (RCT) of PBT vs r-CBT for difficult-to-treat unipolar depression and anxiety disorders. In total, 80 patients are recruited at an outpatient clinic and included in two intervention arms.

Primary outcome is emotional distress, secondary outcomes include psychological well-being and quality of life, adaptive behavior, psychological flexibility, and reflective functioning. Assessments of outcome variables are conducted before and after therapy and at 6 months follow-up. Weekly patient-rated outcomes are collected for every session to investigate process of change. Outcome assessors, blind to treatment allocation, will perform the observer-based symptom ratings, and adherence with manual will be monitored using self-report.

Discussion:

The current study will be the first RCT of PBT in a health care setting. The planned moderator and mediator analyses will clarify the mechanisms of change in psychotherapy and

the association between personalized assessment based on dynamic network analysis and treatment effect.

Trial registration:

Clinicaltrials.gov JWGUniversity record III L5-519/05.000.002. Registered 27 June 2024

Keywords

Process-based Therapy, dynamic network analysis, difficult to treat depression, cognitive behavioral therapy, randomized controlled trial

Administrative information

Title {1}	Process-based Therapy vs. routine-CBT for difficult-to-treat mood and anxiety disorders: Study protocol for a randomized controlled trial
Trial registration {2a and 2b}.	Clinicaltrials.gov JWGUniversity record III L5-519/05.000.002. Registered 27 June 2024
Protocol version {3}	Research protocol, version 02, 23. July 2024.
Funding {4}	This work is funded by the LOEWE Top Professorship for [name] of the Hessian Ministry of Science and Arts.
Author details {5a}	[name], [name], [name], [name], [name], [name], [name], [name]: all Department of Clinical Psychology and Psychotherapy, Goethe University Frankfurt, [name], Germany

	
[name], Department of Clinical Psychology and Translational Psychotherapy, Philipps University Marburg, [name], Germany

Name and contact information for the trial sponsor {5b}
 
Role of sponsor {5c}
	
[name]. [name], [name]; email: [contact]
 
[name]: Principal Investigator of the trial. [name]: funder and Co-Principal Investigator. Study design, interpretation of data. Writing of the report. Decision to submit the report for publication.
 
[name], [name], [name], [name], [name]: trial management and data collection., Writing of the report.
 
[name], [name] : analysis of data. Writing of the report.

Introduction

Background and rationale {6a}

Unipolar depression and anxiety disorders represent the most common mental health problems encountered in mental health care [1]. These conditions frequently lead to prolonged suffering, psychosocial impairment, and substantial socio-economic burdens [2]. Thus, it is of major interest to optimize the efficacy of treatments in mental health services for these disorders.

The results of recent meta-analyses show that CBT is effective for both depression [3] and anxiety disorders [4]. However, it has become evident that remission rates following CBT for depression and anxiety disorders on average still remain slightly under 50% [5], and there has been a debate about the stagnating outcomes of CBT in depression [6] and anxiety disorders [7]. This highlights the importance of optimizing the efficacy of CBT.

One promising way to improve outcome is to personalize treatment by matching the specific mechanisms underlying psychological treatment to the psychological processes contributing to the psychological dysregulation of the individual patient. The process-based approach [8] focuses on this principle by gathering individual data through ecological momentary assessments that are used to develop idiographic dynamic networks to identify the key process maintaining the maladaptive pattern [9], and by choosing interventions which target change processes matching to this key process [10]. In contrast to a latent disease model, which assigns symptoms to an underlying disease, a disorder is seen as an individual network of interacting processes that is maladaptive in specific contexts [11]. However, in an extended evolutionary meta-model, context-bound psychological processes, instead of symptoms, are captured in an ideographic network on different psychological dimensions [12] and change processes are conceptualized according to the basic evolutionary principles of variation, selection and retention [13]. Furthermore, in contrast to syndrome-based treatment packages,

interventions are chosen according to the change processes which have been empirically supported in mediational analysis of RCTs [14].

Given the increased effort needed for the personalization, process-based therapy appears especially relevant for patients who do not respond to empirically supported treatments. In psychiatric care, treatment-resistance is defined as a non-response to an adequate treatment given a correct diagnosis [15]. However, there is a large variety of definitions about the number and type of unsuccessful treatment attempts required to meet the criteria for treatment-resistance, in particular for treatment of depression [16]. To avoid the theoretical difficulties of categorially excluding any response to a treatment, it has been recently suggested to prefer the more comprehensive term ‘difficult-to-treat’ depression [16,17]. In line with this recommendation, a Delphi method-based consensus on the definition of treatment-resistant anxiety disorders [18] proposed the term “difficult-to-treat” anxiety disorder due to its usefulness in the clinical context.

Objectives {7}

The main objective is to investigate the effects of PBT compared with r-CBT for outpatients with difficult-to-treat unipolar depression or anxiety disorders. Primary outcome is emotional distress, secondary outcomes include psychological well-being and quality of life. Apart from the primary and secondary outcomes, we aim to investigate whether PBT, as proposed theoretically, produces changes in psychological flexibility, variation, selection, and retention of adaptive behavior, reflective functioning and capacity for social and interpersonal pleasure. Furthermore, we will examine the possible mediating role of therapists' adherence with the manual and patients' changes in avoidance/ behavioral control and cognitive style on outcome. Lastly, we will investigate potential moderators of outcome, i.e. patient characteristics including treatment expectations and experiential vs. rational learning style, as well as therapeutic alliance, across and within treatment conditions.

The primary outcome measure in this trial is the difference in symptoms of psychological distress between the two groups. We hypothesize that PBT leads to significantly greater reductions in symptoms of emotional distress, as compared to r-CBT after treatment and at 6 month follow-up. Furthermore, we expect that the secondary outcome measures positive mental health and quality of life are significantly more improved following PBT than r-CBT. Based on the treatment targets in PBT, we also hypothesize that variation, selection, and retention of adaptive behavior, psychological flexibility, and reflective functioning will be improved to a significantly higher degree following PBT compared with r-CBT. In addition, we hypothesize that changes in avoidance/ behavioral control and cognitive style significantly mediate a positive outcome. Finally, we expect that a positive treatment expectations and an experiential learning style of the patients, as well as therapist's adherence with the treatment manual, will significantly moderate treatment outcome.

Trial design {8}

The current trial is an investigator-initiated, pragmatic, parallel randomized clinical trial (RCT). Two equally sized intervention arms, PBT and r-CBT, are compared. In total, we include 80 patients recruited from a university outpatient clinic. A CONSORT diagram is provided in Fig. 1.

Fig. 1

Consort Flow diagram of the study design.

EMA: Ecological Momentary Assessment

PBT: Process-based Therapy

r-CBT: Routine Cognitive-Behavioral Therapy

Methods: Participants, interventions and outcomes

Study setting {9}

The study will be conducted within the outpatient clinic at the Department of Psychology, Goethe University Frankfurt.

Therapists are psychologists in advanced training for CBT, who are randomized to either PBT or r-CBT. Therapists randomized to PBT receive 20 hrs. training focusing on personalization of treatment by

- 1) deriving a hypothetical network model of the individual problem,
- 2) guiding patients through the collection of EMA data,
- 3) interpreting dynamic network models,
- 4) drawing network-related treatment decisions, and
- 5) applying interventions based on mechanisms related to the central knot of the network.

Supervision of PBT treatments is offered by the first author. Therapists randomized to PBT receive a manual [19] containing essential procedures in network-based assessment and treatment.

Therapists randomized to r-CBT do not receive additional training and are supervised as usual by supervisors licensed for CBT.

Eligibility criteria {10}

We aim to include 80 patients who meet the inclusion criteria: (1) a primary DSM-5 diagnosis of depressive or anxiety disorder, (2) at least two unsuccessful attempts of pharmacological or psychological treatment according to the German guidelines for the treatment of depression or anxiety disorders (Arbeitsgemeinschaft der Wissenschaftlichen Medizinischen Fachgesellschaften, AWMF), (3) age 18-65 years, (4) sufficient knowledge of the German language. Participating patients are not required to discontinue medication, but to keep medication constant over the treatment period. Patients will be excluded in case of (1) increased suicidality, (2) substance abuse or dependency, (3) diagnose of borderline Personality Disorder, (4) pervasive developmental disorder, psychotic disorder, eating disorder, bipolar disorder, or severe physical illness. Inclusion and exclusion criteria are assessed by intake clinicians using M.I.N.I. [20] adapted for DSM-5. Assessment of failure to respond to adequate treatment is based on an interview focusing on prior treatments and documents available from treating therapists or institutions.

Who will take informed consent? {26a}

Potential trial participants are initially informed about the purpose of the trial by therapists at intake interview after registration at the outpatient clinic of the Department of Psychology. Patients who are interested in a participation receive detailed information from trial management staff about potential benefits and risks; their right to refuse participation and to withdraw consent at any time; institutional affiliation of the trial at the university and sources of trial funding. Written consent is obtained according to the Declaration of Helsinki and as approved by the ethics committee of the Department of Psychology and Sports Sciences at Goethe University Frankfurt.

Interventions

Explanation for the choice of comparators {6b}

Clinical guidelines of the Association of the Scientific Medical Societies in Germany (Arbeitsgemeinschaft der Wissenschaftlichen Medizinischen Fachgesellschaften, AWMF) recommend the application of evidence-based treatment manuals of CBT as standard therapy for patients with anxiety disorders [60] and depression [61]. For patients with treatment failure in the past, no specific recommendations are given, except the adaptation of treatment to possible reasons for nonresponse or, if accepted by the patient, general change in treatment modality (from psychotherapy to pharmacotherapy or reverse). Thus, based on the guidelines cited above, standard interventions for patients with treatment failures do not differ from routine care and usually comprise traditional cognitive and behavioral interventions, but not third wave therapies.

Intervention description {11a}

Both treatments comprise a 9-week baseline phase and a 20-week intervention phase.

Baseline phase: In the PBT condition, a hypothetical network model of the problem is derived and EMA is conducted based on the key components of the model: situational context, cognition, emotion, body symptom, behavior, cognitive processing and motivational schema. Focusing on these dimensions, typical examples of maladaptive responses are determined, and subsequently adaptive counterparts representing the desired poles of the dimensions that should be targeted in the treatment are defined. Then, participants are instructed to apply the mobile app Status (Vacay ©) which prompts the judgement of the seven dimensions established in the hypothetical network model on a bipolar scale ranging from -100 (maladaptive) to +100 (adaptive). Data are gathered in the situational context related to the problem. Therapists guide the adaptation of the items during the weekly sessions and help the

patient to overcome difficulties in identifying situations and entering judgements of the components of the network model. EMA is completed when at least 100 measurements are taken. Then, a dynamic network analysis is computed for assessing autoregressive and cross-lagged effects of the variables [21]. These effects are estimated and visualized in a network representing variables as ‘nodes’, the effects between them as directed arrows (‘edges’) and autoregressive effects as ‘self-loops’.

In the baseline phase of r-CBT, qualitative self-observational data are collected, using unstructured handwritten diaries of situations related to the problem, including notes on behaviors, cognitions and emotions. Therapists assist patients in completing the diaries on a daily basis, support them to deepen the understanding of the problem and derive a behavioral analysis of the individual problem based on the SORKC model according to Kanfer and Saslow (1965; [22]), as required for the application of CBT in German routine mental health care.

Treatment phase: This phase consists of 20 sessions for both treatment conditions. In PBT, treatment is initiated by a collaborative interpretation of the dynamic network model based on EMA collected during the baseline. Therapists are instructed to identify the central node, significant edges, self-loops and positive or negative feedback loops between the nodes [19]. Based on the outcome of the dynamic network model, interventions are selected on the basis of empirical evidence for mechanisms of change matching to the central node of the individual patient, besides feedback loops and self-loops, as the key process maintaining the maladaptive pattern [10]. Interventions are conceptualized in the evolutionary framework as variation, selection and retention of an adaptive mode of the central node related to the specific context of the problem [13]. The change of this variable is monitored using daily judgements on the basis of EMA. Further treatment planning focuses on additional targets to establish the adaptive modes of the dimensions as defined in the positive network model.

In r-CBT, as opposed to PBT, a naturalistic setting is retained for treatment decisions.

Treatment planning follows traditional theories about the effects of the interventions on factors maintaining the disorder, e.g. avoidance and exposure in anxiety disorder or reduced reinforcement of activities and behavioral activation in depression [23]. Interventions are selected on the basis of common treatment manuals related to diagnoses, e.g. CBT for depression. Individual data from the behavioral analysis are used to tailor the techniques to the problem behaviors or dysfunctional thoughts of patients. Treatment process focuses mainly on the implementation of the manualized interventions adapted to the individual patient as recommended in the National guidelines for treatment of depression and anxiety disorders.

Criteria for discontinuing or modifying allocated interventions {11b}

Adverse events will be monitored by the therapists, reviewed by the supervisors and reported to the PIs throughout the trial.

Study treatment must be terminated for one of the following reasons: (a) Withdrawal of patient's consent to study treatment or (b) Study treatment termination by the investigator. Study treatment of a patient will be terminated by the investigator for one of the following reasons: (a) severe serious complications which makes it necessary to stop the study treatment, including acute suicidality or (b) non-compliance with the study protocol. If the investigator terminates the treatment of the patient prematurely, he has to inform the patient about his decision and the primary reason for withdrawal will be recorded in the patient file. If the patient caused the premature withdrawal the data collected before termination may be used if the patient agrees and an informed consent for follow up is signed by the patient. Allocated interventions will be adapted on consultation of the supervisor, in case of worsening of the patient's condition.

Strategies to improve adherence to interventions {11c}

Adherence to interventions will be supported by the strategies included in the treatment manuals. In r-CBT, these strategies include exploration of possible reasons for non-compliance, psychoeducation about the treatment, and clarification of treatment goals. In PBT, exploration of motivational factors, validation of barriers and shared decision making in the selection of interventions will be applied.

Relevant concomitant care permitted or prohibited during the trial {11d}

Psychopharmacological treatment will be permitted if prescribed by a psychiatrist. Concurrent psychotherapy will be prohibited and leads to exclusion from the trial.

Provisions for post-trial care {30}

If continuation of treatment is considered as necessary by the patient and the therapist at post-treatment, patients will be offered psychotherapy in the outpatient clinic.

Outcomes {12}

Primary endpoints

Emotional distress, as assessed by the total score of the DASS-21 [25], represents the primary outcome measure.

Secondary outcomes

Health-related quality of life will be assessed using the international standard Euroqol-5D (EQ-5D; [26]). Positive mental health including emotional, psychological and social aspects of well-being is assessed by the unidimensional Positive-Mental Health Scale (PMH, [27]) with 9 self-report items. The Anticipatory and Consummatory Interpersonal Pleasure Scale (ACIPS; [28]) is a 17-item self-report inventory and will be used to measure the pleasure patients experience in interpersonal situations. Psychological flexibility is measured by the 3-items self-report inventory Acceptance and Action Questionnaire Version 2 (AAQ-2; [29]). The Reflective Functioning Questionnaire (RFQ; [30]) is a 54-item self-report inventory assessing the respondent's ability to understand the internal mental states of self and others.

Mentalizing capacity is divided in two subscales, Certainty and Uncertainty about mental states. The Client Satisfaction Questionnaire (CSQ-8; [31]) is an 8-item self-report instrument constructed to measure satisfaction with health services, which will be used only at post-assessment.

Weekly and daily patients' self-ratings of treatment process

The Process Based Assessment Tool (PBAT; [32]) is a transtheoretical set of 18 self-report items, assessing variation, selection and retention of adaptive behavior. The Depression Anxiety Stress Scale-10 (DASS-10; [33]) is the short version of the DASS-21, a self-report inventory measuring stress, anxiety and depression in three subscales. The Cognitive-Behavioral-Therapy Skills Questionnaire (CBTSQ; [34]) is a 6-item self-report inventory measuring patients' use of cognitive behavioral therapy interventions, with the dimensions behavioral activation and cognitive restructuring.

The Status-PBT (Vacay ©, 2024) is a mobile application for EMA during baseline phase which uses personalized questions and captures six dimensions (thought, emotion, body sensation, behavior, cognitive processing, motivational schema) on bipolar continuous scales ranging from -100 to +100. Similarity of the context with typical problem situations as defined in the hypothetical network model is rated on a continuous scale ranging from 0 to +100.

Therapists' ratings

The Mini International Neuropsychiatric Interview [20] will be applied in the Version 7.0 for DSM-5 and contains 18 modules for the major mental disorders. At the enrolment interview all modules be used to assess inclusion criteria and comorbidity, but the modules anorexia and bulimia nervosa, binge eating and prolonged grief are only carried out in full if there are indications in the interview. The presence of personality disorders is assessed according to the Structured Clinical Interview for DSM 5 for Personality Disorders (SCID-PD [35]).

A check-list of interventions for therapists is used after each session to check adherence, based on literature reviews [36,37] and meta-analyses [38–40]. The Process-based Decision-making Questionnaire (PBDMQ) [24] contains 24 items and was developed to assess adherence with PBT. The “Clinical Global Impression Scale” (CGI; [41]) is 3-item observer-rated scale measuring the clinical impression of the severity of the mental disorder and is used to track changes in symptom severity.

Moderators

The Kolb Learning Style Inventory [KLSI; [42]) will be administered at pre-treatment to assess active experimentation vs. abstract conceptualization learning style. The Credibility/Expectancy Questionnaire (CEQ; [43]) comprises contains 6 items three items of the subscale credibility and another three items of the expectancy subscale. The Helping Alliance Questionnaire (HAQ-11; [44]) comprises 11 items and measures therapeutic alliance. The questionnaire will be completed by patients and therapists at pre- and post-treatment.

Participant timeline {13}

Patients are evaluated by clinicians to be eligible for participation in the study on the basis of inclusion and exclusion criteria described before. If patients are eligible for treatment, they will be provided with information about the project. Patients who consent to participate in the project will be included in the pretreatment assessment (see Table 1). Patients who cannot or will not participate in the study will be offered treatment as usual in the outpatient clinic.

Table 1 Overview of measurements

		Inclusion	Baseline (Sess. 1-9)	Pre- Treatment	Treatment (Sess. 10-30)	Post- Treatment	Follow Up
	Week Instrument	0	1-9	10	11-31	32	57
Therapist	M.I.N.I./ SCID-PD	X					
	CGI	X		X		X	X
	HAQ-11		X week 7	X		X	
	FAMOS	X					
	Intervention Checklist		X week 9		X weekly		
	PBDMQ		X Every 4 weeks		X Every 4 weeks		
Patient	DASS-21	X		X		X	X
	EQ-5D	X		X		X	X
	PMH	X		X		X	X
	ACIPS	X		X		X	X
	AAQ-II	X		X		X	X
	RFQ	X		X		X	X
	PBAT	X		X	X weekly	X	X
	DASS-10				X weekly		
	CBTSQ	X		X	X weekly	X	X
	EMA/diary		X daily week 5-9		X EMA: daily (centralnode)	X EMA: daily week 32-33	
	HAQ-11		X week 7	X		X	
	KLSI			X			
	CEQ			X			
	CSQ					X	

Abbreviations:

M.I.N.I., Mini-International Neuropsychiatric Interview;

SCID-PD, Structured Clinical Interview for DSM 5 – Personality Disorders;

CGI, Clinical Global Impression Scale

HAQ-11, Helping Alliance Questionnaire;

FAMOS, Fragebogen zur Analyse Motivationaler Schemata, Kurzversion (Brief Assessment of Motivational schemata);

DASS-21, Depression Anxiety Stress Scale 10 Items;

EQ-5D, EuroQol 5 Dimensions;

PMH, Positive Mental Health Scale;

ACIPS, Anticipatory and Consummatory Interpersonal Pleasure Scale;

AAQ, Acceptance and Action Questionnaire

KLSI-12, Kolb Learning Style Inventory;

CEQ, Credibility Expectancy Questionnaire;

RFQ: Reflective Functioning Questionnaire;

CSQ-8, Client Satisfaction Questionnaire

PBAT, Process-Based Assessment Tool;

DASS-10, Depression Anxiety Stress Scale 10 Items;

CBTSQ, Cognitive Behavioral Therapy Skills Questionnaire

PBDMQ, Process-based Decision-making Questionnaire

EMA: Ecological Momentary Assessment.

Sample size {14}

Sample size estimation is based on the expected outcome in DASS-21, with treatment condition as between-subjects factor and a within-subjects repeated measurement factor (pre, post, follow-up). Since no previous trial has examined the effects of PBT, the expected effect size is set to a moderate effect of $f = .25$. Using an alpha level (α) of $= .05$ and a power of $= 0.8$ with correlation among repeated measures estimated at $r = 0.4$, 78 patients are needed (39 in each arm) to detect significant differences. To compensate for non-starters, a total sample of 80 patients will be randomized.

Recruitment {15}

The outpatient clinic of the Department of Psychology has previously been engaged in several clinical trials. The number of attending patients is about 1000 patients per year. Thus, adequate participant enrolment can be expected to reach target sample size.

Assignment of interventions: allocation {16}

If eligibility for the study is confirmed, and informed consent to randomization is given, patient will be randomized. To allocate study participants to treatment conditions, a randomization list is created by the data management staff using the statistical software R. The group allocations is printed out individually and placed in sealed envelopes. For each newly included participant, a member of the trial management staff draws an envelope and reads off the group allocation. The same procedure is used to randomize therapists to the treatment conditions.

Blinding {17}

No blinding of participants, care providers, outcome assessors or data analysts after randomization is planned.

Data collection {18}

Plans for assessment and collection of outcomes {18a}: An overview over assessments and collection of outcome during baseline, treatment and follow-up period is given in Table 1 and the instruments are described in section {12}.

Plans to promote participant retention and complete follow-up {18b}: Participant retention during baseline, treatment and follow-ups will be supported by the staff of the trial management. Participants who discontinue or deviate from intervention protocols will be requested to complete questionnaires at the measurement points according to the schedule presented in Table 1.

Data management {19}

The trial will use electronic data collection and documentation, which is hosted by the company Vacay©. Entry of questionnaires will be performed by the participants. Coding, security and storage of data will be ensured by the staff of the trial management. Access to the data is only allowed for persons who are documented as trial personnel and have received a training. The given data will be checked electronically for its plausibility and consistency in a multistage procedure. Detected inconsistencies and missing or implausible data will be clarified with queries (electronically or paper-based) and necessary changes will be carried out. At the end of trial, the database will be closed after data cleaning process. The pseudonymized patient data recorded are stored by Vacay in accordance with legal requirements.

Confidentiality {27}: Personal information about potential and enrolled participants will be pseudonymized and collected, shared, and maintained in accordance with the European data protection regulation.

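### Adverse-event monitoring is promised for the whole trial, but the protocol names only the therapist as collector and gives no means of collection for follow-up or after treatment is terminated

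*Protocol*

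**What the plan says.** Section {11b} of the Protocol gives adverse events one sentence: "Adverse events will be monitored by the therapists, reviewed by the supervisors and reported to the PIs throughout the trial". The same section lists reasons for the investigator to end a patient's treatment, among them "severe serious complications which makes it necessary to stop the study treatment, including acute suicidality". It then requires that the patient be told and the reason recorded.

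Table 1 sets the timeline in weeks: "Week Instrument 0 1-9 10 11-31 32 57". Sessions fill weeks 1–9 and 11–31, post-treatment assessment is week 32 and follow-up is week 57. The table lists interviews, ratings, questionnaires and EMA or diary entries. No row concerns adverse events.

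Three provisions reach beyond the last session:
- The EMA/diary row has the entry "EMA: daily week 32-33".
- The CGI, in the therapist block of Table 1, and most of the patient questionnaires are repeated at week 57. Section {12} says that the CGI "is used to track changes in symptom severity".
- Section {30} provides: "If continuation of treatment is considered as necessary by the patient and the therapist at post-treatment, patients will be offered psychotherapy in the outpatient clinic".

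For patients who stop early, section {18b} says: "Participants who discontinue or deviate from intervention protocols will be requested to complete questionnaires at the measurement points according to the schedule" shown in Table 1.

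**The concern.** The duration promised in {11b} and the means given for it do not match. A therapist who holds weekly sessions can learn of events as they happen. Once the sessions end, or a patient's treatment is terminated, the protocol names no other person, instrument or contact for collecting events.

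Two things are at stake. First, completeness: admissions, suicide attempts or marked deterioration after therapy may never be recorded. Second, selection: patients who continue in the clinic under {30} still have a therapist who can report events, and the others do not. Continuation depends on judged need at post-treatment, so the chance that an event is recorded would depend on outcome, and possibly on arm. Event counts from follow-up could then not be read as a fair description of either arm, in a trial that expects an advantage for PBT at 6 months (section {7}).

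**Working it through.** The protocol states no figure for the period without adverse-event collection. The check is a reading of Table 1 against {11b}, {18b} and {30}, with simple week counts.

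**Inputs (Table 1).** Last session week 31; post-treatment week 32; EMA weeks 32–33; follow-up week 57.

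**Length of follow-up.** 57 − 32 = 25 weeks.

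**Stretch with no scheduled contact.** EMA occupies weeks 32 and 33, and week 57 is an assessment. The empty weeks are 34 to 56: 56 − 34 + 1 = 23 weeks.

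**If the post-treatment EMA is for PBT only.** Section {11a} describes EMA for PBT and handwritten diaries for r-CBT, and the week 32–33 entry names EMA alone. If r-CBT patients have no entry there, their empty stretch is weeks 33 to 56: 56 − 33 + 1 = 24 weeks. The difference is one week, but contact would then differ by arm.

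**Does anything scheduled after week 31 collect adverse events?**

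| Provision | When | What the protocol says it records | Adverse events? |
|---|---|---|---|
| EMA | Weeks 32–33 | Personalized dimensions such as thought, emotion and behavior, and similarity of context | Not described |
| CGI | Weeks 32, 57 | Severity of the disorder | Not described |
| Patient questionnaires | Weeks 32, 57 | Distress, quality of life, well-being, process measures; satisfaction and alliance at week 32 only | Not described |
| Continued therapy, {30} | After week 32 | Not specified; a therapist is present | Possible, but only for those who continue |

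**Patients terminated early.** Section {18b} keeps them on the questionnaire schedule, and the table shows what that covers. No section gives them a contact at which adverse events are asked about. For patients who withdraw themselves, {11b} makes the use of data collected before termination depend on the patient's agreement and a signed consent for follow-up.

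**Result.** From week 32, or from an earlier termination, the only route to an adverse-event record that can be identified in the text is a therapist who happens still to be seeing the patient.

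**The case against.** The strongest reply is that {11b} means what it says. It covers the whole trial and does not tie monitoring to sessions. Table 1 is an overview of measurements, and event reporting runs separately from therapist to supervisor to PI. An operational safety procedure may hold the detail and is not at hand. This stands in part: the text must not be reported as saying that monitoring ends. It does not close the gap, because who collects events once therapy is over is a matter for the protocol, and the only role it names has no scheduled event-collecting contact by then.

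A reader might infer that 25 of 57 weeks are unobserved. That goes too far. EMA runs in weeks 32–33, the CGI and questionnaires fall at week 57, some patients may continue in the clinic, and events can be asked about in retrospect at a visit. For the same reasons, multiplying 25 weeks by 80 patients would give a ceiling and not an estimate: the number who continue under {30} is unknown.

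A reader might also infer that the patients at highest risk are lost from sight. The documents do not support that either, since {18b} keeps those who discontinue on the assessment schedule. What they lack is an adverse-event question or contact.

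Finally, section {7} states no safety objective or hypothesis, and the sample was sized on the DASS-21. It would be wrong to say that this gap defeats a planned safety comparison. The point concerns complete and even recording of harms, not power to compare them.

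**Conclusion.** The concern holds as a gap in specification. Section {11b} promises adverse-event monitoring for the whole trial, and nothing in the protocol delivers it once sessions end by week 31 or treatment is terminated. About 23 weeks (34 to 56) have no scheduled contact, and the EMA, CGI and questionnaires on either side are not described as collecting adverse events. Followed as written, capture in follow-up would depend largely on who stays in therapy under {30}.

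The conclusion rests on three assumptions: that Table 1 lists every scheduled contact; that the week-57 CGI is a severity rating and not an adverse-event interview, as {12} describes it; and that no separate safety procedure names another collector. If such a procedure exists, the remedy is to refer to it in {11b}. No sample size, power or efficacy figure is affected.

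**What to change.** Reconcile {11b}, Table 1 and {18b} in one of two ways.

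1. **Deliver the promise.** Add the same brief adverse-event item set, asking about events since the last assessment, to the week 10, 32 and 57 assessments in both arms. Give it a row in Table 1. State in {18b} that patients who discontinued are asked the same items at the same time points, as far as their consent allows.
2. **Narrow the promise.** Restrict the statement in {11b} to the therapy period, and say in the report that adverse events in follow-up were not collected systematically.

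The first is preferable because it makes recording equal across arms and independent of continued therapy. It costs a few items on assessments that are already scheduled, with questionnaires already entered electronically by participants ({19}), and some staff time to process the answers. Items at weeks 32 and 57 rely on recall, over 25 weeks in the second case, so milder events will be under-reported, but in the same way in both arms. The second costs only wording and leaves follow-up harms unmeasured. How staff should respond clinically to a reported event is for the investigators; no rule is proposed here.
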